4.4.1.4.6 AESIs

AESIs will be collected throughout the study (from the inclusion until the 6 months safety follow-up contact after the last vaccination). AESIs are to be reported as SAEs. Each AESI will be retrieved using the following (as shown in [Table 4.4](#)):

Table 4.4: AESI PTs

AESI	PT
Guillain-Barre syndrome (GBS)	Chronic inflammatory demyelinating polyradiculoneuropathy Demyelinating polyneuropathy Guillain-Barre syndrome Miller Fisher syndrome

AESI	PT
Bell's Palsy	Facial paralysis Facial paresis
Encephalitis/Myelitis (including transverse myelitis)	Myelitis Myelitis transverse Encephalitis is using the narrow SMQ term “Noninfectious encephalitis” (Medical Dictionary for Regulatory Activities [MedDRA 20.1])
Optic neuritis	Optic neuritis Optic neuropathy
Brachial Neuritis	Radiculitis brachial Brachial plexopathy Neuralgic amyotrophy
Convulsions	Febrile Convulsion Seizure

4.4.2 Immunogenicity

4.4.2.1 Computed Values for Analysis

The endpoints for the evaluation of immunogenicity by HAI method are:

For subjects 9 to 17 years of age and previously influenza vaccinated subjects 6 months to 8 years of age:

- HAI antibody (Ab) titers obtained on D0 and D28
- Individual HAI titers ratio D28/D0
- Seroconversion (titer < 10 [1/dil] at D0 and post-injection titer ≥ 40 [1/dil] at D28, or titer ≥ 10 [1/dil] at D0 and a ≥ 4-fold increase in titer [1/dil] at D28)
- Percentage of subjects with titers ≥ 40 (1/dil) at D0 and D28

For previously influenza unvaccinated subjects 6 months to 8 years of age:

- HAI Ab titers obtained on D0, D28, and D56
- Individual HAI titers ratio D28/D0 and D56/D0
- Seroconversion (titer < 10 [1/dil] at D0 and post-injection titer ≥ 40 [1/dil] at D28 and D56, or titer ≥ 10 [1/dil] at D0 and a ≥ 4-fold increase in titer [1/dil] at D28 and D56)
- Percentage of subjects with titers ≥ 40 (1/dil) at D0, D28, and D56

The endpoints for the evaluation of immunogenicity by virus SN method are:

For subjects 9 to 17 years of age and previously influenza vaccinated subjects 6 months to 8 years of age:

- Individual neutralization test (NT) Ab titer on D0 and D28
- Individual NT Ab titer ratio (fold increase in serum NT post-vaccination relative to D0) at D28
- Subjects with NT Ab titers ≥ 20 (1/dil), ≥ 40 (1/dil), ≥ 80 (1/dil) at D28
- Fold-increase in NT Ab titer [post/pre] ≥ 2 and ≥ 4 at D28
- Detectable NT (NT Ab titer ≥ 10 [1/dil]) at D0 and D28

For previously influenza unvaccinated subjects 6 months to 8 years of age:

- Individual NT Ab titer on D0, D28, and D56
- Individual NT Ab titer ratio (fold increase in serum NT post-vaccination relative to D0) at D28 and D56
- Subjects with NT Ab titers ≥ 20 (1/dil), ≥ 40 (1/dil), ≥ 80 (1/dil) at D28 and D56
- Fold-increase in NT Ab titer [post/pre] ≥ 2 and ≥ 4 at D28 and D56
- Detectable NT (NT Ab titer ≥ 10 [1/dil]) at D0, D28, and D56

For HAI and SN assays, in order to appropriately manage extreme values (<lower limit of quantification [LLOQ] and \geq upper limit of quantification [ULOQ]) for analysis purposes, the following computational rule is applied to the values provided in the clinical database for each blood sample (BL) drawn:

- If a value is < LLOQ, then use the computed value LLOQ/2
- If a value is \geq LLOQ and < ULOQ (or \leq ULOQ), then use the value
- If a value is \geq ULOQ (or $>$ ULOQ), then use the computed value ULOQ

For immunogenicity values from HAI assay, each BL will provide two values on each strain on each time point (duplicates). In order to appropriately manage replicate values for analysis purposes, the individual geometric mean (GM) of the 2 values will be computed for each BL after managing extreme values as described above. For immunogenicity values from SN assay, each BL will have one value reported for each strain and each time point.

4.4.2.2 Fold-rise

The derived endpoint fold-rise is driven by both baseline and post-baseline computed values which are computed as described in [Section 4.4.2.1](#). The computed value for fold-rise is:

Computed value = Post-vaccination computed value / Baseline computed value.

For HAI assay, if the computed value is \geq 4-fold rise, then the derived 4-fold rise indicator will be "Yes" for that test, otherwise the corresponding indicators will be "No".

For SN assay, if the computed value is \geq 2-fold rise or 4-fold rise, then the derived corresponding 2-fold rise or 4-fold rise indicator will be "Yes" for that test, otherwise the corresponding indicators will be "No".

Note: If baseline or post-baseline is missing, then the fold-rise is missing.

4.4.2.3 Seroconversion

For HAI assay, seroconversion is defined as either

- A computed value <10 [1/dil] at D0 and post-injection computed value ≥ 40 [1/dil] at D28 and D56 (if applicable), or
- A computed value ≥ 10 [1/dil] at D0 and a \geq 4-fold rise in computed titer values [1/dil] at D28 and D56 (if applicable) as described in [Section 4.4.2.1](#).

4.4.3 Efficacy

No clinical efficacy data will be obtained in the study.

4.4.4 Derived Other Variables

4.4.4.1 Age for Demographics

The age of a subject in the study was the calendar age in months for children under 2 years old, and in years for subjects 2 years and older at the time of inclusion. The age calendar was the age computed automatically in the CRB, and presented as an integer.

4.4.4.2 Duration of the Study

The duration of the study is computed in days as follows:

- Maximum (Visit dates, Termination date, safety follow-up date) – minimum (V01 date)+1

The duration of the active phase of the study is computed in days as follows:

- Maximum (latest date of V03 [or V05 for subjects receiving 2 doses], latest date of termination during the active phase) – minimum (V01 date) +1,

The duration of the 6 months safety follow-up phase of the study is computed in days as follows:

- Maximum (date of D180 [or D208 for subjects receiving 2 doses] safety follow-up) – minimum (V03 dates [V05 dates for subjects receiving 2 doses], termination dates of the active phase) +1.

4.4.4.3 Subject Duration

The duration of a subject in the active phase of the trial is computed as follows:

- Maximum (V03 dates [or V05 dates for subjects receiving 2 doses], termination date) – V01 date +1.

The duration of a subject participation in the trial, including the 6 months safety follow-up, is computed as follows:

- Maximum (visit dates, termination date, safety follow-up date) – V01 date + 1.

4.4.4.4 Time Interval

The time interval between two visits/vaccinations/blood samples is computed as follows:

Later date – earlier date.

4.4.4.5 Influenza Vaccination during the Previous Influenza Season

This information will be used as collected. No derivation or imputation will be done.

5 Statistical Methods and Determination of Sample Size

All statistical analyses will be performed under the responsibility of the Sponsor's Biostatistics Platform using the SAS® software, Version 9.4 or above (SAS Institute, Cary, North Carolina, USA).

The results of the statistical analysis will be available in the final clinical study report (CSR).

For descriptive purposes, the following statistics will be presented:

Table 5.1: Descriptive statistics produced

Baseline characteristics and follow-up description	Categorical data	Number of subjects. Percentage of subjects.
	Continuous data	Mean, standard deviation, quartiles, minimum, and maximum.
Clinical safety results	Categorical data	Solicited: Number and percentage (95% confidence intervals [CIs] of subjects). Unsolicited: Number and percentage (95% CIs) of subjects, and number of events.
Immunogenicity results	Categorical data (seroconversion, cutoff)	Number and percentage (95% CIs) of subjects.
	Continuous data (titer / data)	Log10: Mean and standard deviation. Anti-Log10 (work on Log10 distribution, and anti-Log10 applied): Geometric mean, 95% CI of the geometric mean, quartiles, minimum, and maximum. Graphical representation by Reverse Cumulative Distribution Curve (RCDC).

The CI for the single proportion will be calculated using the exact binomial method (Clopper-Pearson method, quoted by Newcombe (9), ie, using the inverse of the beta integral with SAS®).

For immunogenicity results, assuming that Log10 transformation of the titers / data follows a normal distribution, at first, the mean and the 95% CI will be calculated on Log10 (titers / data) using the usual calculation for normal distribution (using Student's t distribution with n-1 degree of freedom), then antilog transformations will be applied to the results of calculations, in order to provide GMs and their 95% CI.

Rounding rules on descriptive statistics edited will follow the Sanofi Pasteur standard working instruction (“Conventions for the Presentation of Descriptive Statistics”). To present percentages (and 95% CI of percentages), one digit after the decimal place will be used.

5.1 Statistical Methods

5.1.1 Hypotheses and Statistical Methods for the Objectives

5.1.1.1 Hypotheses

No hypotheses for safety and immunogenicity are planned. All analyses are descriptive.

5.1.1.2 Statistical Methods

For the cohorts controlled by the non-adjuvanted QIV-SD, results will be described per stage, according to vaccine received, per age group. Age groups will also be pooled within the same vaccine group for the main endpoints. When age groups are pooled, since age distributions between QIV-HD groups and the pooled QIV-SD group are different, the Simpson Paradox might exist. Therefore, each QIV-HD group (30 μ g, 45 μ g, and 60 μ g) will be compared with its corresponding and restricted QIV-SD group (ie, QIV-SD control group restricted to relevant study groups for comparison to QIV-HD at 30 μ g, QIV-HD at 45 μ g, and QIV-HD at 60 μ g respectively) to reduce the potential bias. If any of the stages are not completed, analyses for the higher dose or next stage will not be performed.

For the cohort controlled by the adjuvanted TIV, results will be described according to vaccine received.

For main safety analyses, results will be described based on both “after any vaccination” and “after each vaccination”.

For main immunogenicity analyses, results will be described based on both “after last vaccination” and “after each vaccination”. Subgroup immunogenicity analyses per previous vaccination status and/or baseline serostatus may be presented when appropriate. Comparison between each QIV-HD group (30 μ g, 45 μ g, and 60 μ g) and the pooled QIV-SD group will also be performed stratified on age groups for immunogenicity endpoints.

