--	---

Planned Sample Size:	
A total of 700 subjects are planned to be enrolled:
 

• Group 1: 40 subjects; 36 months to < 5 years of age (previously influenza vaccinated and unvaccinated subjects)

• n = 30 (QIV-HD: 30 µg HA/strain/dose)

• n = 10 (QIV-SD [unadjuvanted]: 15 µg HA/strain/dose)

• Group 2: 40 subjects; 36 months to < 5 years of age (previously influenza vaccinated and unvaccinated subjects)

• n = 30 (QIV-HD: 45 µg HA/strain/dose)

• n = 10 (QIV-SD [unadjuvanted]: 15 µg HA/strain/dose)

• Group 3: 40 subjects; 6 to < 36 months of age (previously influenza vaccinated and unvaccinated subjects)

• n = 30 (QIV-HD: 30 µg HA/strain/dose)

• n = 10 (QIV-SD [unadjuvanted]: 15 µg HA/strain/dose)

• Group 4: 90 subjects; 36 months to < 5 years of age (previously influenza vaccinated and unvaccinated subjects)

• n = 45 (QIV-HD: 60 µg HA/strain/dose)

• n = 45 (QIV-SD [unadjuvanted]: 15 µg HA/strain/dose)

• Group 5: 40 subjects; 6 to < 36 months of age (previously influenza vaccinated and unvaccinated subjects)

• n = 30 (QIV-HD: 45 µg HA/strain/dose)

• n = 10 (QIV-SD [unadjuvanted]: 15 µg HA/strain/dose)

• Group 6: 60 subjects; 6 to < 36 months of age (previously influenza unvaccinated subjects)

• n = 30 (QIV-HD: 60 µg, 45 µg, or 30 µg HA/strain/dose)*

• n = 30 (QIV-SD [unadjuvanted]: 15 µg HA/strain/dose)

• Group 7: 60 subjects; 6 to < 36 months of age (previously influenza vaccinated subjects)

• n = 30 (QIV-HD: 60 µg, 45 µg, or 30 µg HA/strain/dose)*

• n = 30 (QIV-SD [unadjuvanted]: 15 µg HA/strain/dose)

• Group 8: 60 subjects; 6 to < 24 months of age (previously influenza unvaccinated subjects)

• n = 30 (QIV-HD: 60 µg, 45 µg, or 30 µg HA/strain/dose)*

• n = 30 (adjuvanted TIV: 7.5 µg HA/strain/dose)

• Group 9: 40 subjects; 5 to 8 years of age (previously influenza vaccinated and unvaccinated subjects)

• n = 30 (QIV-HD: 30 µg HA/strain/dose)

• n = 10 (QIV-SD [unadjuvanted]: 15 µg HA/strain/dose)

• Group 10: 40 subjects; 5 to 8 years of age (previously influenza vaccinated and unvaccinated subjects)

• n = 30 (QIV-HD: 45 µg HA/strain/dose)

• n = 10 (QIV-SD [unadjuvanted]: 15 µg HA/strain/dose)

• Group 11: 60 subjects; 5 to 8 years of age (previously influenza vaccinated and unvaccinated subjects)

• n = 30 (QIV-HD: 60 µg, 45 µg, or 30 µg HA/strain/dose)*

• n = 30 (QIV-SD [unadjuvanted]: 15 µg HA/strain/dose)

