### 5.1.2 Justification of the Study Design

QHD04 study will describe the safety of the 3 different dosages of QIV-HD in children 6 months to 17 years of age. The study will also describe the immunogenicity of the different dosages of QIV-HD compared to a unadjuvanted QIV-SD (Fluarix Quadrivalent, licensed in the US) in all stages of the study and compared to an adjuvanted TIV (FLUAD Pediatric, licensed in Canada) during Stage 4 after the highest acceptable dosage of QIV-HD is established. Both comparators will be obtained commercially and will be used according to the approved indication.

Given the different volumes in the 3 different dosages of the QIV-HD and the comparator vaccines, QHD04 will be a staged, modified double-blind study with an unblinded administrator used at each study site. The administrator will not be involved in any of the blinded study assessments (eg, safety).

Since this is the first time that the QIV-HD will be administered to the pediatric population, an ESDR will be performed for subjects 6 months to 8 years of age prior to dosage ascension (30, 45, and 60 µg HA/strain/dose).

Given the matured immune system in children 9 to 17 years of age, no ESDR will occur for subjects 9 to 17 years of age prior to dosage ascension. Subjects 9 to 17 years of age will be randomized to receive the 30 and 45 µg HA/strain/dose vaccines separately from subjects 9 to 17 years of age who receive the 60 µg HA/strain/dose formulation in order to maintain the randomization ratio across all age groups and thus allow for pooling of the 30, 45, and 60 µg HA/strain/dose formulations across all age groups as well.

The comparison of the QIV-HD that will be used in Stage 4 (highest dosage with acceptable safety) to the adjuvanted TIV will be an indicator in terms of expected vaccine efficacy since FLUAD Pediatric is the only licensed pediatric vaccine with studies evaluating both HAI immunogenicity and relative efficacy data.

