Site staff will connect to the IRT, enter the identification and security information, and confirm a minimal amount of data in response to IRT prompts. The IRT will then provide the group assignment and have the site staff confirm it. Stratified randomization will be applied for all

subjects enrolled in each group stratified by previous influenza vaccination status and country. Site will not be a strata for randomization due to the small sample size in each group. The allocation ratios between investigational HD vaccines to the comparators are: 3:1 ratio in groups 1, 2, 3, 5, 9, and 10; 3:3:1 ratio in group 12; and 1:1 ratio in groups 4, 6, 7, 8, 11, and 13. The full detailed procedures for group allocation are described in the Operating Guidelines. If the subject is not eligible to participate in the study, then the information will only be recorded on the subject recruitment log.

Subject numbers that are assigned by the IRT will consist of a 12-digit string (a 3-digit country identifier [840 for the US and 124 for Canada], a 4-digit study site identifier, and a 5-digit subject identifier). For example, Subject 840000100005 is the fifth subject enrolled in Center Number 1 in the US.

Subject numbers should not be reassigned for any reason.

Dose numbers will be 7 digits long. Dose numbers are not used for packaging but only in the IRT system.

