l_1 and u_1 are calculated from the CI of the single proportion in Group A given by:

$$\frac{(2n_1 p_A + Z_{0.025}^2 \pm Z_{0.025} \sqrt{(Z_{0.025}^2 + 4n_1 p_A(1-p_A))})}{2(n_1 + Z_{0.025}^2)}$$

l_2 and u_2 are calculated from the CI of the single proportion in Group B given by:

$$\frac{(2n_2 p_B + Z_{0.025}^2 \pm Z_{0.025} \sqrt{(Z_{0.025}^2 + 4n_2 p_B(1-p_B))})}{2(n_2 + Z_{0.025}^2)}$$

where $Z_{0.025}$ is the upper 97.5th percentile of the standard normal distribution.

When age stratification is considered, the age-stratified GMT ratio between each QIV-HD group (30 μ g, 45 μ g, and 60 μ g) and the pooled QIV-SD group will be reported. The corresponding 95% CIs of GMT ratios will be calculated using an analysis of variance (ANOVA) model of \log_{10} -transformed titers considering vaccine group as the main effect and age group as a covariate.

The 95% CI of the difference in seroconversion rates between each QIV-HD group (30 μ g, 45 μ g, and 60 μ g) and the pooled QIV-SD group will also be stratified on age effect and calculated using the Wald method (normal approximation). Weighted average of the difference over strata will be calculated using the Minimal Risk weights method (11). The details are as follows.

The 100(1- α)% two-sided CI for the difference in proportions between two groups A and B using the Minimum Risk Weights will be in the form:

$$\hat{\delta}_w \pm Z_{\alpha/2} \sqrt{\left\{ \sum_{i=1}^s w_i^2 \hat{V}(\hat{\delta}_i) \right\}}$$

Where $\hat{\delta}_w = \sum_{i=1}^s w_i \delta_i$ is the estimated weighted average of the proportion difference over strata; $\delta_i = \hat{p}_{iA} - \hat{p}_{iB}$ is the estimated proportion difference between group A and B at stratum i ($i=1, \dots, s$);

$\hat{V}(\hat{\delta}_i) = \frac{\hat{p}_{iA}(1-\hat{p}_{iA})}{n_{iA}} + \frac{\hat{p}_{iB}(1-\hat{p}_{iB})}{n_{iB}}$ is the estimated variance of proportion difference between group A and B at stratum i , where n_{iA} and n_{iB} are the sample sizes of group A and B at stratum i ;

$Z_{\alpha/2}$ is the $100(1 - \alpha/2)$ th percentile of the standard normal distribution;

w_i is the weight assigned at stratum i , where $\sum_{i=1}^s w_i = 1$.

The Minimum Risk method computes the weights w_i as follows:

$$w_i = \frac{\beta_i}{\sum_{k=1}^s V_k^{-1}} - \left(\frac{\alpha_i V_i^{-1}}{\sum_{k=1}^s V_k^{-1} + \sum_{k=1}^s \alpha_k \delta_k V_k^{-1}} \right) \left(\frac{\sum_{k=1}^s \delta_k \beta_k}{\sum_{k=1}^s V_k^{-1}} \right)$$

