5.5 Determination of Sample Size and Power Calculation

QHD04 is a Phase II study to describe the safety and immunogenicity of 3 different dosages of QIV-HD. The sample size is not powered. The study will include a total of approximately 700 subjects that will be divided into 13 groups as follows:

- Groups 1, 2, 3, 5, 9, and 10 will each include 40 subjects (previously influenza vaccinated or previously influenza unvaccinated) in a 3:1 ratio (QIV-HD: QIV-SD).
- Group 4 will include 90 subjects (previously influenza vaccinated or previously influenza unvaccinated) in a 1:1 ratio (QIV-HD: QIV-SD).
- Groups 7 will include 60 subjects who are previously influenza vaccinated in a 1:1 ratio (QIV-HD: QIV-SD).
- Groups 6 and 8 will each include 60 subjects who are previously influenza unvaccinated in a 1:1 ratio (QIV-HD: QIV-SD or TIV).
- Group 11 and 13 will each include 60 subjects (previously influenza vaccinated or previously influenza unvaccinated) in a 1:1 ratio (QIV-HD: QIV-SD).
- Group 12 will include 70 subjects (previously influenza vaccinated or previously influenza unvaccinated) in a 3:3:1 ratio (QIV-HD: QIV-HD: QIV-SD).

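### If Stage 4 uses 30 or 45 µg, the restricted QIV-SD comparison for that dosage is unbalanced on age (50% versus 70% aged 6 to <36 months) and carries no age adjustment

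*SAP*

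**What the plan says.** SAP 5.1.1.2 states: "Age groups will also be pooled within the same vaccine group for the main endpoints". It then warns that "since age distributions between QIV-HD groups and the pooled QIV-SD group are different, the Simpson Paradox might exist". Its remedy is to compare each dosage "with its corresponding and restricted QIV-SD group (ie, QIV-SD control group restricted to relevant study groups for comparison to QIV-HD" at 30, 45 and 60 µg). It does not list the relevant study groups.

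The design was built to support this pooling. Protocol 5.1.2 explains that the 9 to 17 year subjects are split into two groups "in order to maintain the randomization ratio across all age groups and thus allow for pooling". Protocol 6.5 fixes the allocation at 3:1 in Groups 1, 2, 3, 5, 9 and 10, and then "3:3:1 ratio in group 12; and 1:1 ratio in groups 4, 6, 7, 8, 11, and 13".

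Protocol Table 5.1 leaves the QIV-HD dosage of Groups 6, 7 and 8 open at 30, 45 or 60 µg, to be settled by the early safety reviews.

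The estimators are in SAP 5.1.1.2.2. Without age stratification, they are a crude GMT ratio and a Wilson-score interval for the seroconversion difference. The age-stratified methods start at "When age stratification is considered, the age-stratified GMT ratio between each QIV-HD group" and are written for the pooled QIV-SD group. SAP 5.1.1.2.1 describes safety by single proportions.

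**The concern.** Restricting the controls to the same study groups equalises the age mix only if every study group at a dosage has the same ratio of QIV-HD to QIV-SD. That is so at 30 and 45 µg in Stages 1 to 3 (30 to 10 in every age group) and at 60 µg throughout (1:1). It stops being so if 1:1 groups of the youngest children join a pool of 30-to-10 groups. This happens if Stage 4 uses 30 or 45 µg, a path the documents provide for.

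On that path the comparison offered as protection against Simpson's paradox becomes open to it, and it is reported with crude estimators. If children of 6 to <36 months respond less, the control group is pulled down and QIV-HD looks better with no vaccine effect. The study is meant to inform the dosage for Phase III, so a pooled ratio that moves with age mix alone matters even in a descriptive study.

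**Working it through.** **Plan's own total.** SAP 5.5: 6×40 + 90 + 60 + 2×60 + 2×60 + 70 = 700, as stated.

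**Inputs** (Protocol Table 5.1 and 6.5; SAP 5.5), QIV-HD : QIV-SD:
- 30 µg: Groups 1, 3, 9 at 30:10 each; Group 12 has 30 at this dosage and 10 QIV-SD.
- 45 µg: Groups 2, 5, 10 at 30:10 each; Group 12 has 30 at this dosage and the same 10 QIV-SD.
- 60 µg: Groups 11, 13 at 30:30 each; Group 4 at 45:45.
- Stage 4 dosage: Groups 6, 7 at 30:30 each, all 6 to <36 months. Group 8 has no QIV-SD arm and is left out.

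**Reading used.** Groups 6 and 7 join the pool for the dosage they receive. This follows from pooling age groups within a vaccine group, but the SAP does not state it.

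**Age mix**, in the order 9–17 y / 5–8 y / 36 m to <5 y / 6 to <36 m (Stage 3 completed):

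| Stage 4 dosage | Comparison | QIV-HD | Restricted QIV-SD | Share 6 to <36 m |
|---|---|---|---|---|
| 60 µg | 30 µg and 45 µg, each | 30/30/30/30 | 10/10/10/10 | 25% v 25% |
| 60 µg | 60 µg | 30/30/45/60 | 30/30/45/60 | 36.4% v 36.4% |
| 45 µg | 45 µg | 30/30/30/90 | 10/10/10/70 | **50% v 70%** |
| 45 µg | 30 µg | 30/30/30/30 | 10/10/10/10 | 25% v 25% |
| 30 µg | 30 µg | 30/30/30/90 | 10/10/10/70 | **50% v 70%** |
| 30 µg | 45 µg | 30/30/30/30 | 10/10/10/10 | 25% v 25% |
| 30 or 45 µg | 60 µg | 30/30/45/0 | 30/30/45/0 | 0% v 0% |

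The imbalance is 20 points (90/180 against 70/100). After a completed Stage 3 the whole QIV-SD pool has 80/235 = 34.0% in this band, a gap of 16 points in the other direction. On this path restriction makes the imbalance larger.

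**Bias with no vaccine effect.** Crude log10 GMT difference = (0.50 − 0.70) × (−log10 k), where k is the fold by which GMT at 6 to <36 months falls below the other bands. So the crude ratio is k^0.20. The documents give no k; the values below are assumptions.
- k = 1: 1.00
- k = 1.5: 1.08
- k = 2: 1.15
- k = 3: 1.25
- k = 4: 1.32

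**Coverage of the nominal 95% interval.** The sampling error of the crude difference is s√(1/180 + 1/100), with s the within-age log10 SD. The interval's half-width is 1.96 times the same root times the pooled SD, which also carries the age spread. For k = 2, coverage is about 86% at s = 0.5 and 90% at s = 0.7. For k = 4 it is about 63% and 77%. Both SDs are assumptions.

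**Proportions.** Bias = 0.20 × the age difference in rate: 2, 4 or 8 points for an age difference of 10, 20 or 40 points.

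**Remedies checked.** Keeping Groups 6 and 7 out of the pool restores 30/30/30/30 against 10/10/10/10, with no imbalance. Keeping them in and fitting vaccine group plus age group gave a simulated ratio of 1.00, against 1.25 crude (k = 3, s = 0.6, no vaccine effect).

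**The case against.** The strongest reply is that the plan already adjusts for age. SAP 5.1.1.2 and 5.1.1.2.2 provide an age-stratified comparison of each dosage with the pooled QIV-SD group, a sensitivity analysis adding baseline titer, and results per age group. This stands for immunogenicity: an age-adjusted result will appear beside the crude one on every path. It does not repair the crude restricted comparison, which may contradict it, and it does not extend to safety.

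Second, the relevant study groups are not listed. If they mean Stages 1 to 3 only, there is no imbalance. That is a fair point, but the pooling rule points the other way, and listing the groups is needed under either reading.

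Third, the problem is contingent. The SAP drops analyses for the next stage when a stage is not completed, which may close off the route that skips Stage 3. It does not cover a lower dosage chosen after a completed Stage 3. The protocol's optional two-country 60 µg pool presumes 60 µg in Stage 4, but the design tables still allow all three dosages.

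Fourth, all analyses are descriptive and unpowered, so no formal decision rests on the crude ratio. That stands and limits the weight of the point.

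A reader might also infer a second route to imbalance from the synopsis sample-size list, which gives Group 11 as "n = 30 (QIV-HD: 60 µg, 45 µg, or 30 µg HA/strain/dose". The documents do not support this. Table S1, Table 5.1, Protocol 5.1.1 and 6.5, and the SAP list only 60 µg for this group. The footnote attached to that line concerns Stage 4, whereas Group 11 is in Stage 3. Enrollment of this age group stops if Group 10 fails its review. It is an inconsistency to reconcile and adds no bias mechanism.

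**Conclusion.** The point holds for one comparison on a planned but contingent path. If Stage 4 uses 30 or 45 µg and Groups 6 and 7 are pooled with the other groups at that dosage, the restricted comparison sets 50% against 70% aged 6 to <36 months. With no vaccine effect, an assumed 2- to 4-fold lower GMT in that band produces a crude ratio of about 1.15 to 1.32 in favour of QIV-HD. With no age effect the bias is zero.

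Three stronger readings are not supported:
- It does not follow that every restricted comparison fails unless Stage 4 uses 60 µg. Only the dosage used in Stage 4 is affected.
- It does not follow that the plan lacks a valid comparison for that dosage. The age-stratified and per-age-group immunogenicity results remain valid.
- The documents do not say that the crude restricted ratio would decide which dosage goes to Phase III.

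What remains unprotected is the crude restricted comparison itself and any pooled safety proportions set against the restricted group. The SAP should be amended.

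**What to change.** In SAP 5.1.1.2, list the study groups in each restricted comparison for each possible Stage 4 dosage. For a Stage 4 dosage of 30 or 45 µg, state one of the following:
- Groups 6 and 7 are reported separately from the Stage 1 to 3 pool, which leaves 25% per age band in both arms; or
- they are included, and the restricted GMT ratio comes from the age-group ANOVA already written in 5.1.1.2.2.

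If they are included, use an age-stratified method for the seroconversion difference that tolerates sparse strata. The planned Minimum Risk weights use the inverse of a Wald variance. That variance is zero, and the weight undefined, when both arms of a stratum are at 0% or 100%. Three of the four restricted control strata would have only 10 subjects.

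Describe pooled safety for that dosage by age group or with the same group restriction.

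Separately, as an editorial point, reconcile the Group 11 dosage in the synopsis sample-size list with Table S1, Table 5.1 and Protocol 5.1.1.

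The cost is SAP wording and, at most, a further run of a planned model and a stratified interval. No subjects or data are added, and the age term introduces no bias on the 60 µg path.
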